1.2 Strategies to Prevent Early Thrombosis of Native Fistulae

Several approaches have been considered to improve the early patency of native fistulae. Pre-operative examination using venography, ultrasound, or arteriography, may identify the best location for creation of native fistulae in patients with vasculature that is suboptimal for supporting fistula maturation²¹. While such studies are utilized in many centers, there is not strong evidence that their use increases the number of functioning fistulae, and, in fact, performance of these diagnostic tests may discourage attempts at fistula creation among patients with a reduced but potential likelihood of attaining a suitable native fistula.

Identification of risk factors for fistula thrombosis has been attempted by several investigators²³⁻²⁷. Many of the predictors of thrombosis such as age, gender, diabetes, race, low blood pressure, and longer dialysis treatment times are both controversial and not readily amenable to modification. Consistent associations between laboratory abnormalities and vascular access thrombosis have not been demonstrated in the few studies examining them^{22,23}. Thus, at present, targeting specific risk factors for modification is not a feasible approach to the problem of early fistula thrombosis.

Similarly, several factors have been identified as predicting adequacy of AV fistulas. Miller et al¹⁴ found that overall only 47 (46.5%) of 101 fistulas placed over a two year period matured adequately to be used at a blood flow ≥ 350 ml/min. The adequacy was lower if age ≥ 65 years old (30.0%, $P=0.03$), in diabetics (35.0%, $P=0.061$), and if BMI ≥ 27 (34.5%, $P=0.07$). Furthermore, the adequacy of forearm fistulae were particularly poor in women (7%), age ≥ 65 years old (12%), and diabetics (21%), and the authors recommended the creation of upper arm fistulae in such patients. They felt that their lower overall rates of access maturation were due to attempting fistulae in patients who previously might have received grafts. Although this study indicates that the use of the upper arm may increase the development of adequate fistula, it will be difficult to achieve the rates of fistula use suggested in current guidelines.

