5. DATA COLLECTION

5.1 Baseline Data

The baseline evaluation is designed to ensure that subjects meet the inclusion/exclusion criteria, to obtain information regarding demographics, access history, dialysis prescription, and medical history that may affect treatment response and risk of access thrombosis, and to obtain a laboratory evaluation to ensure that patients are not at risk for developing complications of therapy. Data should be collected as close to the time of fistula creation as possible but no longer than 45 days prior, and should include:

1. Demographic Data – age, gender, racial/ethnic background.
2. Medical History – cause of ESRD, diabetes mellitus, hypertension, myocardial infarction, angina, congestive heart failure, cerebrovascular accident or transient ischemic attack, claudication, amputation, smoking history, deep venous thrombosis or pulmonary embolism, nephrotic syndrome, significant bleeding event within past year, peptic ulcer disease.
3. Height and weight (for determination of body mass index).
4. Access History – number, type, and location of any previous accesses.
5. Dialysis History – date of initiation of chronic dialysis, if currently on dialysis.
6. Current Medications
7. Blood Pressure (sitting) – For patients already on dialysis, this should be a pre-dialysis, mid-week measurement.
8. Laboratory Data – CBC. For patients on dialysis, the blood should be drawn pre-dialysis. Laboratory tests should be done no longer than 45 days prior to randomization.
9. Quality of life

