5.3 Six Weeks After Fistula Creation

1. Fistula Anatomy – date of surgery, site of anastomosis (e.g., wrist, elbow), inflow artery, outflow vein.
2. Fistula Patency – presence of bruit throughout systole and diastole ≥ 8 cm proximal to the arteriovenous anastomosis
3. Current Medications
4. Intercurrent /Adverse Events – drug reactions, side effects, hospitalizations, death, access procedures (fistulogram, angioplasty, thrombectomy, conversion to graft, ligation of draining veins), abnormal laboratory values, or other complications. The occurrence of any such events should be reported as close to the time the event occurred as possible;

however, the review at this study visit should minimize the possibility that such events go unrecognized or unreported. Patients will be instructed at enrollment to inform study personnel immediately if a bleeding event occurs.

5. If dialysis was initiated via the new fistula prior to this six-week study visit the date of initiation of dialysis should be recorded.
6. Procedures performed on fistula (fistulogram, angioplasty, thrombectomy, conversion to graft, ligation of draining veins), and dates of such procedures.
7. Study Drug Use – reason for and duration of study drug interruption. Remaining study drug should be returned at this visit and pill count performed.
8. Quality of life

For patients with fistula thrombosis and no restoration of patency during the six week study drug administration period, all of the above data (#'s 1-8) will be collected at the earlier of the following: six weeks after fistula creation or at the end of study participation (30 days after discontinuation of study drug).

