8.2.2.2 Outcome Measures

Primary Analysis of Fistula Patency at 6 Weeks

The primary analysis will evaluate the effect of randomization to clopidogrel vs. placebo on the probability that a new fistula will be patent six weeks after randomization. This analysis will be carried out by applying the Mantel-Haenszel test to compare the proportion of patent fistulas at six weeks with stratification for Clinical Center and the location of the fistula. The comparison of the clopidogrel and placebo interventions in the primary analysis will be carried out using an intent-to-treat strategy in which patients are retained in their randomized groups regardless of their compliance to the treatments. A 2-sided hypothesis test will be conducted at the 5% level of significance.

Analyses of Secondary Outcomes

The Mantel-Haenszel test (with stratification for Clinical Center and fistula location) will also be used to evaluate the effect of randomization to clopidogrel on the two main secondary outcomes:

- a. the proportion of fistulae suitable for dialysis with or without radiological or surgical modification in the two treatment groups (secondary outcome measure).
- b. the proportion of fistulae suitable for dialysis without radiological or surgical modification in the two treatment groups (secondary outcome measure).

Other Secondary Analyses

Secondary analyses will include an analysis of the three outcome measures for patients in whom study drug is not deliberately discontinued during the six week study drug administration period. Study outcomes will also be analyzed using logistic regression and adjusting for additional covariates found by interactive data analysis to be predictive of the primary or secondary outcomes. Death rates in active drug and placebo groups will also be compared.

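### The supportive logistic regression takes its covariates from an interactive search of the trial's own outcomes; a fixed list of baseline variables would be better and costs almost nothing

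*Protocol*

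**What the plan says.** Under Other Secondary Analyses, section 8.2.2.2 states: "Study outcomes will also be analyzed using logistic regression". It then describes the choice of covariates for this model as "adjusting for additional covariates found by interactive data analysis to be predictive of the primary or secondary outcomes". It gives no candidate list and no numerical criterion. It does not say who selects, or whether that person sees treatment assignment, and it sets no limit on when a candidate must have been measured.

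The analyses ranked above this one are fixed. The primary analysis is specified as "applying the Mantel-Haenszel test to compare the proportion of patent fistulas at six weeks with stratification for Clinical Center and the location of the fistula", under intention to treat, two-sided at 5%. For the two suitability outcomes, "The Mantel-Haenszel test (with stratification for Clinical Center and fistula location) will also be used".

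The protocol also has the material for a fixed list. Section 1.2 discusses "Many of the predictors of thrombosis such as age, gender, diabetes, race, low blood pressure" and longer treatment times, and reports age, diabetes and BMI in relation to fistula adequacy. Section 5.1 sets up the baseline evaluation "to obtain information regarding demographics, access history, dialysis prescription, and medical history that may affect treatment response and risk of access thrombosis". Variables arising after randomization are collected too: section 5.3 lists "Study Drug Use – reason for and duration of study drug interruption" and access procedures, and section 5.4 adds first cannulation and first dialysis.

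**The concern.** The sentence is more than a detail left for an analysis plan. It prescribes a method, and a plan that fixed the covariates would have to depart from it. Two analysts could both comply and report different adjusted effects.

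Two consequences need separating. First, if the treatment estimate is visible while the model is built, the model can drift toward a preferred result, and the nominal p-value no longer describes the procedure. Second, a criterion of predicting the outcome favours variables close to the outcome. Some of those collected are its consequences or components. Section 4.4.6 stops study drug after confirmed thrombosis, section 6 defines the primary outcome as unassisted patency, and section 7.2 counts a modified fistula as failed. Adjusting for such a variable can remove or distort part of the treatment effect.

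This is the only covariate-adjusted treatment comparison that the protocol describes, and it covers the primary and both suitability outcomes. A reader would probably use it to judge whether the main result survives adjustment.

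**Working it through.** **The plan's own figures.** The protocol gives no figure for the adjusted model. The sample size in section 8.1 rests on an unadjusted comparison of proportions. With 3% drop-in and 3% drop-out, 25% and 17.5% become 0.25 − 0.03 × 0.075 = 0.24775 and 0.175 + 0.03 × 0.075 = 0.17725. The formula is n = [1.960 √(2p̄q̄) + 1.036 √(p₁q₁ + p₂q₂)]² / (p₁ − p₂)², which gives 604 per arm. Then 604 / 0.95 × 1.027 = 653 per arm, 1306 in total, which is 1.7% above the stated 1284. The stated figure is reproduced closely enough, and nothing in it depends on covariates. The analysed number is about 1284 × 0.95 ≈ 1220, used below.

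**Check 1: selection among baseline covariates, no treatment effect.** The numbers of candidates, their strengths and the sets of models are assumptions.

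*Simulation A:* 1,500 trials, 12 candidates, 3 truly prognostic. Rejection rates at 0.05:
- fixed list: 5.3%
- screen at p<0.10 on outcome prediction: 5.1%
- most favourable of 13 nested models: 7.2%

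The Monte Carlo standard error is √(0.05 × 0.95 / 1500) = 0.56 points, so the first two cannot be told apart.

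*Simulation B:* 4,000 trials per row, 5 prognostic candidates, Monte Carlo standard error 0.34 points.

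| Candidates | Log-OR per SD | Fixed list | Screen p<0.05, ignoring treatment | Best of 11 nested models | Median largest/smallest OR |
|---|---|---|---|---|---|
| 15 | 0.20 | 5.2% | 5.1% | 6.7% | 1.03 |
| 15 | 0.35 | 4.5% | 4.6% | 6.8% | 1.05 |
| 25 | 0.35 | 5.5% | 5.3% | 8.5% | 1.06 |
| 15 | 0.50 | 4.4% | 4.4% | 8.2% | 1.07 |

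A shorter run (1,500 trials, 15 candidates, log-OR 0.35, best of 16 nested models) gave 9.1% against 6.1% for the fixed list. All methods ran high in that sample, including 5.9% unadjusted.

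**Check 2: a post-randomization covariate.** The true failure rates are 25% and 17.5%, so the unadjusted odds ratio is (0.175/0.825) / (0.25/0.75) = 0.636. Assume an event M that occurs in a share m of placebo patients and 0.7m of clopidogrel patients, with failure probability 0.6 when M is present. To keep the marginal rates, the failure rates without M are c₀ = (0.25 − 0.6m)/(1 − m) and c₁ = (0.175 − 0.42m)/(1 − 0.7m). There were 2,000 trials of 1,220 patients per row.

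| m | c₀ / c₁ | Unadjusted OR (power) | OR adjusted for M (power) |
|---|---|---|---|
| 10% | 21.1% / 14.3% | 0.635 (89%) | 0.662 (80%) |
| 20% | 16.3% / 10.6% | 0.637 (88%) | 0.706 (61%) |
| 30% | 10.0% / 6.2% | 0.631 (90%) | 0.775 (33%) |

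The adjusted effect moves toward 1 because part of the benefit runs through M. With another kind of covariate the direction could differ.

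**The case against.** The strongest reply is that little depends on this model. It sits in the lowest tier of analyses, no alpha or decision rule rests on it, and the protocol does not name it as the robustness check. That stands, and it limits the severity.

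A reader might infer that outcome-driven selection by itself invalidates the p-value. The figures do not support this: a screen that ignores treatment holds type I error near 5%, and adjusted odds ratios across baseline-only sets differ by a median factor of only 1.03 to 1.07.

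A reader might also infer that the protocol plans to choose the model by its treatment result. It does not say so. The criterion is prediction of outcomes; choosing with the treatment estimate in view is permitted by silence, not prescribed.

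Nor does the protocol say that drug interruption or procedures will enter. The missing baseline restriction is also silence, and an unseen analysis plan could supply it. Section 5.1 even describes baseline information as "medical history that may affect treatment response and risk of access thrombosis". But nothing ties the model to those variables, and the criterion as written would readily pick up consequences of thrombosis.

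Finally, section 1.2 calls several of these predictors controversial, and its BMI result is one study's P=0.07. That is some reason to search empirically, and it makes the exact list a matter of judgement. It does not prevent a list from being fixed in advance.

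**Conclusion.** The point holds as a low-severity improvement to a supportive analysis. The stated rule is analyst-dependent, does not require selection blind to the treatment estimate, and does not confine candidates to variables set before randomization. The Mantel-Haenszel tests of the primary and two main secondary outcomes, their significance level and the sample size are untouched, so the documents do not support reading this as a threat to the trial's main conclusions.

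Among baseline covariates, the cost is negligible if selection ignores treatment. It is about 2 to 4 percentage points of type I error if the model is picked with the treatment result in view. The larger exposure is a post-randomization covariate: under the assumed mediator, power in the adjusted model falls from about 89% to between 80% and 33%, so a real benefit could seem to vanish on adjustment. That range depends on the assumed frequency of the mediator and its link to failure, neither of which the protocol gives.

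**What to change.** Replace the clause in section 8.2.2.2 with a pre-specified logistic model containing treatment, Clinical Center, fistula location and a fixed list of baseline variables already collected under section 5.1. Examples are age, sex, race, diabetes, BMI, baseline systolic blood pressure, dialysis status at fistula creation and prior access. The exact list is the sponsor's choice, made before unblinding. State that no post-randomization variable enters, and label any data-driven model exploratory.

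The cost is a sentence or two, with no new data and no change to the sample size or the main tests. The downside is that an unanticipated strong predictor would appear only in the exploratory model.

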8.3 Data Quality Control at the Data Coordinating Center

The DCC will regularly provide feedback on measures of the quality of its own performance, including rates of computer down time, rates of randomization of ineligible patients, and time it takes for the DCC to make corrections to the database once a clinical center has responded to a data discrepancy inquiry.

9. TREATMENT EFFECTS AND SAFETY MONITORING

An External Advisory Committee (EAC), composed of independent experts in the fields of nephrology, biostatistics, and clinical trials, will review the accumulating data with regard to

safety and efficacy. The members of the EAC are not involved in the conduct of the trial and have no affiliation with the drug manufacturers. Summary reports of the EAC will be submitted to all IRBs involved in the trial.

The EAC may terminate the trial early if one of the interventions (clopidogrel or placebo) is shown to be superior at an interim analysis based on the statistical stopping guideline (Section 8.2.1). The EAC will also consider comparisons of potential adverse events between the treatment arms. Conditional power calculations and estimates of the recruitment rate will also be provided at interim analyses so that the EAC can assess whether the trial should be terminated early in the event of unexpectedly low recruitment or trends in the treatment group comparison indicating futility of continuation of the study.

Serious adverse events are those that result in any of the following outcomes: death, a life-threatening adverse experience, inpatient hospitalization or prolongation of existing hospitalization, a persistent or significant disability/incapacity, or a congenital anomaly or birth defect. All serious adverse events are reported to the DCC within 24 hours of study personnel learning of the event. Information not available at the time of the initial report will be submitted to the DCC as a follow-up report. The DCC will be responsible for distributing safety reports to the Clinical Centers, the EAC, and NIDDK. NIDDK will submit safety information to the FDA. Summary reports of adverse events will be submitted to all IRBs monitoring the trial. Additional reporting to IRBs will be performed according to local IRB policy. Non-serious adverse events will be reported to the DCC using the appropriate data forms.

10. REGULATORY CONSIDERATIONS

10.1 Institutional Review Boards (IRBs)

The protocol will be submitted to the IRB of each Clinical Center for review and approval. Centers may not recruit patients into the trial until approval of the protocol by their IRB. Protocol amendments and changes will be submitted to the IRB and approval must be received before implementation. All patients enrolled in the trial must sign and date an IRB-approved consent form and medical records release form before any study related procedures are undertaken. Study personnel will explain the study and answer all of the patient's questions before asking the patient to sign and date the consent form.

10.2 Confidentiality of Patient Data

All patient data will be maintained in a secure location. Data collected from study evaluations will be identified by study identification codes. Identifying features including names and addresses will be provided to the DCC, but kept in a secure file separate from the study database. Social Security numbers will be provided to the DCC only with additional written consent from the patient, if required by the local IRB. If such consent is obtained, the Social Security number will be kept in a secure file separate from the study database and will be used to obtain patient-specific hospitalization, medical procedures, and death data from databases other than those maintained for this trial. Patients can withdraw consent for continued access to such databases at any time. Clinically relevant information obtained as a result of participation in this trial may be placed in the patient's medical record as progress notes.

11. PILOT STUDY

Prior to conducting the full-scale trial detailed in Sections 1-10, a pilot study will be performed to evaluate the feasibility of performing the full-scale trial. Because the Clinical Centers are comprised of multiple and geographically disparate sites, and because many of the patients eligible for enrollment in the study will not yet be on chronic dialysis, one of the most challenging aspects of the full-scale trial will be identification of eligible patients. An additional challenge will be to perform both randomization to treatment arm and study drug delivery within the time constraints of the full-scale trial protocol. Thus, the pilot study is designed to evaluate the following specific logistical issues:

1. Ability of centers to identify and enroll patients
2. Ability of centers to randomize and provide study drug to enrolled patients within one calendar day following fistula creation surgery

11.1 Pilot Study Design and Overview

The pilot study is an open-label trial in which patients scheduled to undergo creation of a new upper extremity native fistula will be randomized to receive clopidogrel or no study drug for six weeks following fistula creation surgery. Randomization will be on a 7:3 active drug: no drug allocation, and will be stratified by Clinical Center. The sample size is 50 patients (10 patients per Clinical Center) to be enrolled over a nine week period. For patients randomized to the clopidogrel arm, study drug administration will begin within one calendar day following native AV fistula creation and continue for six weeks following surgery. Fistula patency will be evaluated by physical examination six weeks after fistula creation. Participation in the pilot study will end at the 30-day follow-up telephone call to the patient following the six-week evaluation. The study outcomes include: number of patients enrolled by each Clinical Center during the nine week enrollment period, distribution of patient enrollment from the multiple sites comprising each Clinical Center, proportion of enrolled patients that are randomized within one calendar day following fistula creation surgery, proportion of patients randomized to clopidogrel that receive drug supply within one calendar day following fistula creation surgery, and proportion of patients in the clopidogrel arm who remain on the study drug for the entire six-week drug administration period.

11.2 Pilot Study Enrollment and Randomization

Patients will be recruited from the hemodialysis and chronic renal failure populations of the participating Clinical Centers. The goal of each Clinical Center will be to enroll a total of ten patients. Each Clinical Center should enroll patients from as many of the individual sites comprising the Clinical Center as possible. No more than five patients should be enrolled from the “main” site (i.e., the site of the Clinical Center’s principal investigator), and at least one patient should be enrolled from any site at which anticipated enrollment in the full-scale trial is twenty patients or greater. Identification of potential study participants and the informed consent process will occur as outlined for the full-scale trial (see Section 3).

11.2.1 Pilot Study Eligibility Criteria

Inclusion and exclusion criteria are listed below. Eligibility criteria are the same as for the full-scale trial (see Section 3.1) except that in the pilot study patients do not need to have an anticipated start of hemodialysis within six months of enrollment or be expected to stay at a participating dialysis facility for at least six months.

Inclusion Criteria

1. Age equal or greater than that at which consent can be obtained without parental involvement (18-21 years depending on state regulations).
2. Life expectancy of at least six months.
3. Planned creation of native upper extremity AV fistula.
4. The patient is not on aspirin, or the patient is on aspirin but has not had a myocardial infarction or a cerebrovascular accident within the past 12 months.
5. The patient's physician(s) will allow the patient to participate.
6. Ability to give informed consent.

Exclusion Criteria

1. Women must not be pregnant, breast feeding, or plan to be pregnant during the course of the study.
2. The presence of ongoing bleeding.
3. The presence of a known bleeding disorder (e.g., hemophilia or von Willebrand's disease).
4. Recent bleeding episode requiring transfusion within 12 weeks of entry.
5. The presence of acute ulcer disease. Acute ulcer disease is defined as a new diagnosis of peptic disease including esophagitis, gastritis, or ulcer or the initiation of treatment with proton pump inhibitors, H2 blockers or therapy for Helicobacter pylori within three months prior to obtaining consent.
6. A condition which prohibits discontinuation of anticoagulant drugs, aspirin, nonsteroidal anti-inflammatory drugs, or glucocorticoids during the six week study drug administration period. Use of heparin during dialysis is allowed.
7. Current unstable angina.
8. Required use of clopidogrel.
9. Known hypersensitivity to clopidogrel.
10. Medical considerations making anti-platelet therapy dangerous.
11. Current uncontrolled hypertension with systolic blood pressure in excess of 200 mm Hg or diastolic blood pressure in excess of 115 mm Hg at the time of enrollment.
12. Baseline platelet count less than 75,000/mm³.
13. Prolonged prothrombin time (INR >1.5) or partial thromboplastin time (5 or more seconds above upper limit of normal).
14. Known advanced liver disease with decompensated cirrhosis, jaundice, ascites or bleeding varices.
15. Current problem with substance abuse.
16. Concurrent participation in another medical intervention trial.
17. Anticipated non-compliance with medical care based on physician judgment.
18. Patient refusal.

